2.2.3.1 Summary of Studies in the Olokizumab Clinical Program

Study RA0001

Study RA0001 was a Phase I, randomized, double-blind, placebo-controlled, dose-escalating, first-in-human study that investigated the safety and tolerability, PK, and pharmacodynamics (PD) of IV OKZ in 67 healthy Caucasian male subjects (33 on active drug and 34 on placebo) with a 99-day follow-up.

Study RA0010

Study RA0010 was a Phase I/IIa study to characterize the PK/PD relationship between systemic OKZ exposure and CRP suppression, following single-dose IV and SC OKZ administration to subjects with RA and to evaluate the safety and tolerability of single doses of OKZ in RA subjects over a therapeutic dose range (as defined by CRP suppression).

Study RA0074

Study RA0074 was a Phase I study in healthy Japanese subjects undertaken to evaluate the PK, PD, safety, and tolerability of SC OKZ prior to undertaking clinical studies in Japanese subjects with RA.

Studies RA0056 and RA0057

Study RA0056 was a Phase II, multicenter, randomized, double-blind, placebo- and active-controlled study of OKZ in 221 subjects in the United States (US) and Europe with active RA who had previously failed TNFi therapy, administered SC at various doses and frequencies to evaluate the efficacy relative to placebo. Eligible subjects were randomized to 1 of 9 treatment groups: OKZ 60 mg SC once every 2 weeks (q2w), OKZ 60 mg SC once every 4 weeks (q4w), OKZ 120 mg SC q2w, OKZ 120 mg SC q4w, OKZ 240 mg SC q2w, OKZ 240 mg SC q4w, placebo SC q2w, placebo SC q4w, and tocilizumab 8 mg/kg IV q4w.

Study RA0057 was the long-term OLE study of RA0056, which was open for enrollment of subjects who had completed the Week 12 visit of Study RA0056. A total of 190 subjects in Study RA0057 received SC injections of OKZ 120 mg q2w throughout the study, regardless of their treatment assignment in RA0056.

Studies RA0083 and RA0089

Study RA0083 was a Phase II, multicenter, randomized, double-blind, placebo-controlled, dose-ranging study of OKZ in 119 Asian subjects with moderately to severely active RA who had previously failed TNFi therapy and were on a stable dose of MTX. Eligible subjects were randomized to 1 of 6 treatment groups: OKZ 60 mg q2w, 60 mg q4w, 120 mg q2w, 120 mg q4w, or placebo q2w, all administered SC.

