2.2.3.2 Summary of Safety Data from Olokizumab Studies

Study RA0001

There were no deaths or serious adverse events (SAEs) reported during the study and no subject discontinued the study as a result of an adverse event (AE). The overall incidence of treatment-emergent adverse events (TEAEs) was slightly higher in the placebo group overall (18 subjects [52.9%]; 35 events) than in the OKZ treatment groups overall (11 subjects [33.3%]; 26 events). No increase in the incidence of TEAEs was observed with increasing dose of OKZ.

The most commonly reported TEAEs were in the system organ classes (SOCs) of gastrointestinal (GI) disorders, general disorders, and infections and infestations. The incidence of GI disorders was similar in both the OKZ group overall (12.1%) and the placebo group overall (11.8%); however, at the preferred term (PT) level, abdominal distension (1 subject [3.0%]), abdominal pain (1 subject [3.0%]), and vomiting (2 subjects [6.1%]) were only seen in the OKZ group. The most frequently reported TEAEs (occurring in ≥3% of subjects in any treatment group) by PT were influenza-like illness (11.8% placebo, 6.1% OKZ), headache (11.8% placebo, 3.0% OKZ), nasopharyngitis (8.8% placebo, 3.0% OKZ), rhinitis (8.8% placebo, 0.0% OKZ), diarrhea (5.9% placebo, 3.0% OKZ), and vomiting (0.0% placebo, 6.1% OKZ).

For the majority of hematology and clinical chemistry parameters there were no clinically significant differences in mean actual values between the placebo group and OKZ treatment groups, and no clinically significant fluctuations in mean actual values over time.

Study RA0010

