Three additional subjects experienced TEAEs leading to permanent discontinuation of OKZ (bladder cancer, palmar pustular dermatitis, and cholecystitis chronic). These subjects were not represented within the patient data sets or tables as this additional information was based on source documentation received from the respective study sites after the clinical database had been locked.

Treatment-emergent AEs were reported by 178 subjects (93.7%). The most commonly reported TEAEs (>10% of subjects) were in the SOCs of infections and infestations; musculoskeletal and connective tissue disorders; GI disorders; investigations; general disorders and administration site conditions; respiratory, thoracic and mediastinal disorders; skin and SC tissue disorders; injury, poisoning and procedural complications; nervous system disorders; metabolism and nutrition disorders; and vascular disorders.

When considering TEAEs by CTCAE grade, the majority of subjects had CTCAE Grade 1 (85.8%) and/or Grade 2 (56.3%) TEAEs. At the SOC level, infections and infestations was the TEAE that occurred most frequently (68.4% of subjects), with a maximum intensity of mild (102 subjects [53.7%]; 239 events), moderate (58 subjects [30.5%]; 103 events), and severe (14 subjects [7.4%]; 17 events). At the PT level, CTCAE Grade 3 TEAEs that occurred in ≥2 subjects included cellulitis, pneumonia, staphylococcal infection, urinary tract infection, back pain, RA, pulmonary embolism, and chest pain. No CTCAE Grade 3 TEAE was reported by more than 3 subjects for any PT. A total of 93 subjects (48.9%) reported TEAEs (281 events) that were judged as related to the study treatment by the Investigator. The TEAE most frequently assessed as being drug-related by the Investigator was injection site reaction SOC (21 subjects [11.1%]; 29 events).

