7.4.3.5 Injection Site Reactions

An injection site reaction is any untoward medical event occurring at the injection site during or after study treatment administration that can be at least possibly attributed to the study treatment (i.e., the relationship cannot be ruled out).

An assessment of pain, redness, swelling, induration, hemorrhage, and itching at the injection site will be performed. At all specified visits (see Table 1), the assessment of injection site reactions that have occurred since the previous visit will be made by the Investigator prior to any administration of study treatment. Injection site reactions noticed after on-site study treatment administration, when the subject is still on site or already at home and recorded

them in their diary, will be also reported. All local reactions that are observed will be monitored until they resolve.

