9.4 Statistical Methods

This section provides a high-level description of the analyses planned in this study. Details of any analysis, interim or final, will be specified in the SAP, to be written and finalized prior to database lock. The statistical analysis will be performed by R-Pharm International's designee. All statistical analyses will be conducted using SAS® version 9.2 or higher for Windows.

All data collected in the clinical database will be presented in subject data listings.

Data collected after the modification of background therapy (as described in Section 6.13.3) will be used in all analyses.

Data collected during the core studies for subjects enrolled in the OLE study may be programmatically combined with the OLE study database for selected analyses.

All analyses of safety and efficacy will be descriptive; no inferential analyses will be performed.

Continuous endpoints will be summarized using descriptive statistics such number of available values (n), mean, median, minimum, maximum, and standard deviation in each treatment group and overall, as appropriate. Categorical endpoints will be summarized by the number and percentage of subjects in each category.

Data will be summarized based on treatment groups reflecting randomized or actual treatment (for efficacy or safety analyses, respectively) during the core and OLE studies as follows:

- a. OKZ 64 mg q4w (OLE): All subjects in the OKZ 64 mg q4w group in the OLE
- b. OKZ 64 mg q2w (OLE): All subjects in the OKZ 64 mg q2w group in the OLE
- c. OKZ 64 mg q4w (core/OLE): Subjects from the OKZ 64 mg q4w group in the core study and continuing on OKZ 64 mg q4w in OLE. For subjects enrolling from the CL04041025 core study, inclusion in the OKZ 64 mg q4w group in the core study will be based on the initial treatment period prior to Week 16 (i.e., placebo subjects re-randomized to receive OKZ 64 mg q4w at Week 16 will not be included in this group).
- d. OKZ 64 mg q2w (core/OLE): Subjects from the OKZ 64 mg q2w group in the core study and continuing on OKZ 64 mg q2w in OLE. For subjects enrolling from the CL04041025 core study, inclusion in the OKZ 64 mg q2w group in the core study will be based on the initial treatment period prior to Week 16 (i.e., placebo subjects

re-randomized to receive OKZ 64 mg q2w at Week 16 will not be included in this group).

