9.4.6.1.1 Analysis of Treatment-Emergent Adverse Event Rates per 100 Patient-years of Follow-up

Summaries of TEAEs occurring in subjects in the safety population of this OLE study will also be provided based on combined AE data from the core studies and the OLE study, attributing each TEAE to the last study treatment received at/before the AE onset. In other words, an AE will be defined as treatment-emergent under a given study treatment (OKZ 64 mg q4w, OKZ 64 mg q2w, placebo, or adalimumab) if AE's onset date is on or after the date of first dose the corresponding treatment and prior to initiation of the next study treatment, if any (e.g., OKZ after placebo or adalimumab). In order to account for differences in the duration of exposure and follow-up under each study treatment and across subjects, subject IRs and ERs will be summarized per 100 subject-years (SY) of follow-up (/100 SY) based on the OLE safety population and presented by study treatments as follows:

- i. OKZ 64 mg q4w: subjects receiving OKZ 64 mg q4w during the core study or OLE. Only those TEAEs that first occur or worsen in severity after the first administration of OKZ 64 mg q4w (either in the core or OLE study) will be counted.
- ii. OKZ 64 mg q2w: subjects receiving OKZ 64 mg q2w during the core study or OLE. Only those TEAEs that first occur or worsen in severity after the first administration of OKZ 64 mg q2w (either in the core or OLE study) will be counted.
- iii. Placebo: subjects receiving placebo during the core study. Only those TEAEs that first occur or worsen in severity after the first administration of placebo and prior to administration of OKZ will be counted. Subjects are considered as receiving placebo during the core study if they are receiving placebo as their overall study treatment, and not as monthly placebo injections administered to maintain the blind in the OKZ 64 mg q4w group.
- iv. Adalimumab: subjects receiving adalimumab as active control study treatment during the core study CL04041023. Only those TEAEs that first occur or worsen in severity after the first administration of adalimumab and prior to administration of OKZ will be included.

The following summaries will be provided:

- IRs (/100 SY) and ERs (/100 SY) for TEAEs overall and by SOC
- IRs (/100 SY) and ERs (/100 SY) for SAEs overall and by SOC and PT
- IRs (/100 SY) and ERs (/100 SY) for AESIs overall and by SOC and PT

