- IRs (/100 SY) and ERs (/100 SY) for (adjudicated) MACE and individual MACE components
- IRs (/100 SY) and ERs (/100 SY) for most frequent TEAEs (PT level IRs [/100 SY] ≥5.0 in any treatment group) by SOC and PT

IRs/100 SY for each specific AE term (referred to as "event" for brevity) under treatment j, corresponding to treatments (i) – (iv) described above, will be calculated as follows:

$$IR_j (/100 SY) = s_j / \sum_i c_{i,j}$$

where s_j is the number of subjects with the event that is treatment-emergent under treatment j, and $c_{i,j}$ is a truncated follow-up time (in 100-year units) for subject i and treatment j (i.e., the time from the subject's date of first dose of treatment j to the date of first occurrence of the event after start of treatment j or end of follow-up period for treatment j, whichever

occurs earlier). For OKZ treatments (OKZ 64 mg q4w and q2w), the end of follow-up period will be the date of last dose of OKZ treatment plus 155 days (5 half-lives of study treatment) or last contact with the subject, whichever occurs earlier. For placebo and adalimumab treatments, the end of follow-up period will be the day before the start of OKZ treatment.

ERs (/100 SY) for each specific AE term under treatment j will be calculated as follows:

$$ER_j(100 SY) = \sum_i v_{i,j} / \sum_i t_{i,j}$$

where $v_{i,j}$ is the number of treatment-emergent events that the subject i experiences under treatment j, and $t_{i,j}$ is a total follow-up time (in 100-year units) of subject i for treatment j, i.e., from the date of subject's first dose of treatment j to the end of follow-up period for treatment j. For OKZ treatments (OKZ 64 mg q4w and q2w), the end of follow-up period will be the date of last dose of OKZ treatment plus 155 days (5 half-lives of study treatment) or last contact with the subject, whichever occurs earlier. For placebo and adalimumab treatments, the end of follow-up period will be the day before the start of OKZ treatment.

Assuming the event process is Poisson distributed, exact $100*(1-\alpha)\%$ confidence intervals for IR_i (/100 SY) and ER_i (/100 SY) will be calculated as follows (Sahai and Khurshid, 1993):

Lower confidence limit:
$$LCL = \frac{\chi^2_{\alpha/2,2D}}{2E}$$
 for D>0, 0 otherwise,

Upper confidence limit
$$UCL = \frac{\chi^2_{1-\alpha/2,2D+2}}{2E}$$

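### Event-rate confidence intervals assume Poisson counts although repeat events in one subject are counted, so they are too narrow for frequent and aggregated adverse-event rows

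*Combined protocol and SAP*

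**What the plan says.** Protocol Section 9.4.6.1.1 defines two follow-up-adjusted rates per 100 subject-years. The IR numerator is the number of subjects with the event, and follow-up is cut at the first occurrence. The ER numerator is the sum over subjects of all treatment-emergent events, and follow-up is not cut.

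One pair of chi-square limits serves both, introduced by "Assuming the event process is Poisson distributed". With D and E the numerator and denominator of the rate, the limits are χ²(α/2; 2D)/(2E) and χ²(1−α/2; 2D+2)/(2E). No value of α is given.

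ERs are planned for adverse events overall and by system organ class, serious events, the most frequent preferred terms, MACE and events of special interest: "IRs (/100 SY) and ERs (/100 SY) for AESIs overall and by SOC and PT". Infections and injection site reactions are both on the special-interest list in Section 7.4.3. Section 4.1 names ERs for serious events and events of special interest as safety endpoints.

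The section mentions no robust variance, negative binomial model or overdispersion check. It does plan cumulative mean function plots for recurrent events, but gives no variance method for them, and they do not alter the ER limits.

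**The concern.** The limits depend only on the total count D. They are right if that total has variance equal to its mean, which holds when all subjects share one underlying rate and events are independent. If some subjects have many events and others none, the total has variance φ times its mean with φ above 1, and the interval should be about √φ times wider. The IR escapes this because each subject contributes at most one event.

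Long-term safety is the primary objective, and the rates will be shown side by side for olokizumab q4w, q2w, placebo and adalimumab. Intervals that are too short would make common-event rates look better determined, and possibly more distinct between regimens, than the data support.

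**Working it through.** The plan states no event count, interval width or α, so there is no figure of its own to reproduce. Two-sided α = 0.05 is assumed. For a truly Poisson total the printed limits work: coverage is 97.5%, 95.3% and 95.5% at 10, 50 and 360 expected events. The question is whether adverse-event totals are Poisson.

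**Inputs (Sections 2.2.3.1 and 2.2.3.2)**
- RA0001: "33 on active drug and 34 on placebo) with a 99-day follow-up". Adverse events: "OKZ treatment groups overall (11 subjects [33.3%]; 26 events". Placebo had 35 events in 18 subjects.
- RA0057, N = 190, infections: "infections and infestations was the TEAE that occurred most frequently (68.4% of subjects), with a maximum intensity of mild (102 subjects [53.7%]; 239 events". Adding 103 moderate and 17 severe events gives 239 + 103 + 17 = 359 events in 68.4% of subjects (130). Severe infections: 17 events in 14 subjects.
- RA0057 drug-related injection site reactions: "injection site reaction SOC (21 subjects [11.1%]; 29 events". The drug-related restriction matters little, because Section 7.4.3.5 itself defines the reaction through "study treatment administration that can be at least possibly attributed to the study treatment (i.e., the relationship cannot be ruled out".
- RA0057 drug-related adverse events: 281 events in 93 subjects.

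**Formulas**
- μ = events/N. Subjects affected under a common Poisson rate = N(1 − e^(−μ)).
- Negative binomial: solve (1 + μ/k)^(−k) = observed event-free share for k. Then φ = 1 + μ/k.
- Width ratio = √φ. Actual coverage = 2Φ(1.96/√φ) − 1.

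**Worked example, infections.** μ = 359/190 = 1.889. Poisson predicts 190(1 − e^(−1.889)) = 161.3 subjects (84.9%) affected; 130 were. The event-free share of 0.316 gives k = 1.255, φ = 1 + 1.889/1.255 = 2.51, √φ = 1.58 and coverage 78%.

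| Row | Subjects affected: observed / Poisson | φ | Width ratio | Coverage |
|---|---|---|---|---|
| RA0001 olokizumab | 11 / 18.0 | 3.35 | 1.83 | 72% |
| RA0001 placebo | 18 / 21.9 | 1.81 | 1.35 | 86% |
| RA0057 infections | 130 / 161.3 | 2.51 | 1.58 | 78% |
| RA0057 severe infections | 14 / 16.3 | 1.36 | 1.16 | 91% |
| RA0057 injection site reactions | 21 / 26.9 | 1.66 | 1.29 | 87% |
| RA0057 drug-related events | 93 / 146.7 | 4.11 | 2.03 | 67% |

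**Chance.** Allocating the observed events at random to equally followed subjects gives as few affected subjects in under 0.01% of runs for RA0001 olokizumab, about 2.6% for RA0001 placebo and about 0.03% for injection site reactions.

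**Unequal follow-up.** RA0001 has one stated 99-day follow-up. RA0057's follow-up distribution is not given, and variation in it also produces event-free subjects.
- If follow-up is uniform from 0 to twice its mean, φ = 1 + (4/3)μ/k after re-solving for k. Infections: φ = 1.8, coverage 86%, width ratio 1.3. Injection site reactions: φ = 1.6, coverage 87%, width ratio 1.3.
- Gamma-shaped follow-up explains the whole excess if its coefficient of variation is 1/√k. That is 1/√1.255 = 0.89 for infections, 1/√0.476 = 1.45 for drug-related events and 1/√0.2305 = 2.08 for injection site reactions.

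**Simulation.** Settings: 940 subjects (half of 1880), RA0057 means and k, full follow-up of 104 weeks + 155 days = 2.42 years, and an assumed 25% early stoppers spread uniformly from 0.5 year. The planned interval covered 79% (infections), 87% (injection site reactions) and 91% (severe infections). A subject-level robust interval covered about 95% in all three and was 1.60, 1.28 and 1.15 times as wide.

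Giving an assumed 35% of subjects the shorter follow-up of switchers (80 weeks from first to last dose + 155 days = 1.96 years) left planned coverage at 78%, 87% and 91%.

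In sparse rows (k = 0.25) the planned interval covered 98%, 97%, 95% and 94% at 5, 10, 20 and 40 expected events.

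**The case against.** The strongest reply is that little turns on this. Section 9.4 states: "All analyses of safety and efficacy will be descriptive; no inferential analyses will be performed". No test or decision uses the limits, and where clustering is strongest the intervals are already tight. Limits relative to the point estimate at 940 subjects, using exp(±1.96√(φ/D)) for the adjusted ones, are:
- infections (1.889 × 940 ≈ 1776 events): planned 0.95–1.05, adjusted 0.93–1.08;
- injection site reactions (about 143 events): planned 0.84–1.18, adjusted 0.81–1.24;
- severe infections (about 84 events): planned 0.80–1.24, adjusted 0.78–1.28.

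This stands and limits the consequence. It does not make the stated confidence level true.

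The evidence also has limits. RA0057 used 120 mg q2w. RA0001 was in healthy men with doses pooled. The 359 infections are summed over intensity rows whose subject counts overlap (102 + 58 + 14 = 174, against 130 affected). For infections alone, follow-up variation could in principle explain everything. No earlier data bear directly on events of special interest overall; that row is inferred from its components. These points make the decimals approximate, but RA0001 and the injection site rows do not depend on the infection figures.

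Finally, the Poisson assumption is disclosed, and IRs and cumulative mean plots appear alongside the ERs, so clustering will be partly visible. A separate SAP, not in the supplied text, might adjust for it. As written, however, the protocol prescribes this formula for every ER.

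**Conclusion.** The concern holds. Exact Poisson limits are appropriate for IRs and adequate for sparse ERs, but too narrow for ERs of frequent or aggregated events. On RA0057-type clustering, nominal 95% intervals would cover roughly 79% for infections, 87% for injection site reactions and 91% for severe infections, and should be about 1.6, 1.3 and 1.15 times as wide. For infections the range runs from 78% under equal RA0057 follow-up, through 86% under uniform follow-up, to nominal if follow-up had a coefficient of variation of 0.89.

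These sizes assume α = 0.05 and that clustering in the earlier studies carries over to this one. The direction is well supported; the exact size for this trial is unknown. It is a reporting error about precision on a listed safety endpoint. It does not bias the rates and affects no decision rule. It should be fixed before database lock.

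**What to change.** In Section 9.4.6.1.1 and the SAP:
1. State α.
2. Keep the exact Poisson limits for IRs.
3. For ERs, use ER × exp(±z × SE) with SE² = Σ(vᵢ − ER·tᵢ)² / (Σvᵢ)², where vᵢ and tᵢ are subject i's events and follow-up. A negative binomial model with a log follow-up offset is an alternative; name one of them in advance.
4. Keep exact Poisson limits for sparse ER rows under a pre-specified rule, for example fewer than 20 events in total or no subject with more than one event. With the robust interval elsewhere, this rule covered 94–98% in every simulated scenario.

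The cost is one paragraph and a few lines of code. The downside is wider intervals for common events and two interval methods to footnote in the same tables. Point estimates, data collection and conduct do not change.

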9.4.6.1.2 Time to First Major Adverse Cardiovascular Event

For MACEs and individual components of MACE, time from the first dose of OKZ to first event will be summarized using a Kaplan-Meier product limit method. This analysis will be

based on the OLE Safety population using combined data from the core studies and the OLE study.

Time to first event will be computed for each specific type of event (MACE overall and individual components of MACE) as the number of days between the subject's date of first dose of OKZ treatment either in the core or OLE study and the onset of the first event that is treatment-emergent under the OKZ treatment. Subjects not experiencing an event of interest during the follow-up period associated with the OKZ treatment will be censored at the date of last contact.

Summaries will be presented by treatment groups, as defined in Section 9.4. Summaries will include plots of the estimated survival curves using the Kaplan-Meier method as well as Kaplan-Meier cumulative estimates of event-free rates at time points corresponding to 6, 12, 18, 24, and 30 months after initiation of OKZ treatment. Pointwise confidence intervals for these estimates will be computed using the log-log transformation method. Kaplan-Meier estimates of mean event-free time and its log-log transformed confidence interval in each treatment group will also be produced. A time limit of 127 weeks will be used for the estimation of mean event-free time if the largest observed time in data is censored. Descriptive statistics for the number of subjects with event, censored, and duration of follow-up for censored subjects will be provided.

Additional details will be provided in the SAP.

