7.4 Safety

Safety assessments will consist of monitoring and recording all AEs, including SAEs, nonserious AESIs, and pregnancies; measurement of safety laboratory assessments; measurement of vital signs, ECGs, physical examinations; and other tests that are deemed critical to the safety evaluation of the study in all subjects who receive at least 1 dose of study treatment. As discussed in Section 7.4.2.3, any pregnancy that occurs while a subject is enrolled in the study will also be monitored and reported according to the appropriate regulations.

The Investigator remains responsible for following, through an appropriate health care option, AEs that are serious and nonserious that caused the subject to discontinue before completing the study. Any AE, including any AE still ongoing at the end of the study, should be followed until it has resolved, it has a stable sequelae, the Investigator determines that it is no longer clinically significant, or the subject is lost to follow-up. If no follow-up is provided, the Investigator must provide a justification.

In addition to records of observations made at specific times, unexpected signs and symptoms and concomitant medications will be recorded in the clinical study records throughout the study. The Investigator will also collect completed pages of the Subject Diary (see Section 5.5) at Visits 2 (Week 26) through 10 (EoT/Week 106), and the Investigator will review any complaints, signs, or symptoms experienced by the subject in association with administration of study treatment. Completed pages of the Subject Diary will serve as source documents, and information will be recorded on the appropriate pages of the eCRF. The Subject Diary will not be used during the Safety Follow-Up Period. Further routine medical assessments in addition to those specified in Table 1 may take place during the study as clinically indicated (e.g., chest X-rays to investigate lung lesions, ECG, etc).

Safety measures in this study include, but are not limited to, SAEs, AEs, vital signs, body weight, and laboratory evaluations, and if required, this information must be present in the AE/SAE report made by the Investigator.

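### Three end rules for OKZ follow-up disagree after day 155, and the 30-month Kaplan-Meier estimate (24-month in four groups) lies beyond scheduled follow-up

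*Combined protocol and SAP*

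**What the plan says.** Protocol Section 9.4.6.1.1 assigns an AE to a treatment if the "AE's onset date is on or after the date of first dose the corresponding treatment and prior to initiation of the next study treatment". No study treatment follows OKZ, so for OKZ this window has no end. In both rate formulas of the same section, OKZ follow-up time ends at the "date of last dose of OKZ treatment plus 155 days (5 half-lives of study treatment) or last contact with the subject, whichever occurs earlier".

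Section 9.4.6.1.2 measures time from first OKZ dose to "the onset of the first event that is treatment-emergent under the OKZ treatment". Subjects with no event "during the follow-up period associated with the OKZ treatment will be censored at the date of last contact". The 155-day cap is not repeated there. Results are given by the Section 9.4 groups at "time points corresponding to 6, 12, 18, 24, and 30 months after initiation of OKZ treatment". If the largest observed time is censored, mean event-free time is limited to 127 weeks. Section 9.4.6.1.3 treats time to first malignancy in a similar manner.

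The data-collection rules also matter:

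- Section 7.4.1 records AEs up to the subject's last visit.
- Sections 7.4.2 and 7.4.5.2 collect SAEs for 22 weeks after the last dose. Later SAEs need reporting only if the investigator thinks they may be related.
- Section 7.4 adds: "Any AE, including any AE still ongoing at the end of the study, should be followed until it has resolved". Contact can therefore continue after the last scheduled visit.

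**The concern.** An event count, its person-time and the censoring date should all refer to one observation period. Here one rule is open-ended, one is capped, and one runs to a contact date that may pass the cap. Take a first MACE on day 158 after the last dose, with last contact on day 161. The event definition in Section 9.4.6.1.2 counts it. The next sentence refers to the OKZ follow-up period. If that means the capped period of Section 9.4.6.1.1, the subject had no event in it and is censored on day 161, after the event. In the rates, the same event enters the numerator with no person-time behind it. Two programmers could code this differently and both claim to follow the text.

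The landmark times are a separate problem: they appear to run past the end of the study. Long-term safety is the primary objective (Section 3.1) and time to first MACE is a named safety endpoint (Section 4.1), so both points touch core outputs.

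**Working it through.** **Plan's own figures.** The half-life is about 31 days (Section 5.2.2), and 5 × 31 = 155 days, as stated. The last visit, SFU-3, is at Week 126 with a window of ±7 days: 126 × 7 + 7 = 889 days = 127.0 weeks, which reproduces the 127-week limit.

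**Where the rules part.** SFU-3 is 22 × 7 = 154 days after the last dose, with window days 147 to 161.

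- On the nominal day, last contact (154) comes before the cap (155). AE recording, person-time and censoring all end together.
- At the latest permitted day the gap is 161 − 155 = 6 days. That is 6/889 = 0.67% of follow-up for subjects starting OKZ at Week 0, and 6/721 = 0.83% for those starting at Week 24.
- If all 1880 subjects were seen on day 161, the excess would be 1880 × 6 / 365.25 = 30.9 subject-years. The total would lie between 1880 × 721 / 365.25 = 3,711 (all Week-24 starters) and 1880 × 889 / 365.25 = 4,576 (all Week-0 starters).
- The documents give no MACE rate. Assuming 0.25 to 2 per 100 subject-years, 30.9 subject-years would yield 0.08 to 0.62 events.
- Contact after SFU-3 to follow an ongoing AE would widen the gap. The documents do not allow this to be quantified.

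**Landmarks.** The last dose is at Week 104 (Section 5.2), and one month is taken as 365.25/12 = 30.44 days.

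| Groups | OKZ start | Start to last dose | Plus 155 days | Months | With SFU-3 on day 161 |
|---|---|---|---|---|---|
| c, d | Week 0 | 104 × 7 = 728 d | 883 d (126.1 wk) | 29.0 | 889 d, 127 wk, 29.2 mo |
| g, h | Week 16 | 88 × 7 = 616 d | 771 d (110.1 wk) | 25.3 | 777 d, 111 wk, 25.5 mo |
| e, f, i, j | Week 24 | 80 × 7 = 560 d | 715 d (102.1 wk) | 23.5 | 721 d, 103 wk, 23.7 mo |

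- 30 months = 913.1 days = 130.4 weeks. This is 30.1 days past the 883-day maximum and 24.1 days past the plan's own 127-week limit.
- 24 months = 730.5 days. Groups e, f, i and j fall 15.5 days short of it, or 9.5 days short with the visit window. Groups c, d, g and h reach it.
- 18 months = 547.9 days, within reach of every group.
- The 127-week limit exceeds windowed follow-up by 127 − 111 = 16 weeks in g and h, and by 127 − 103 = 24 weeks in e, f, i and j.

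Section 5.1 equates about 130 weeks with 2.5 years, but that total includes Screening, before any OKZ. It does not rescue the 30-month landmark.

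**Sensitivity.** A further 10 days of slippage beyond the SFU-3 window would give 899 days (29.5 months) in c and d, still short of 30 months. In e, f, i and j it would give 731 days, past 24 months by half a day.

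**The case against.** The best reply is that the text creates little or no bias. A reader might infer that time after day 155 can add survivors but never events, so that late event-free rates are too high while the incidence rates are also too high. The documents do not support this. It requires the 155-day cap, which is stated for the rate formulas, to limit which events count in Section 9.4.6.1.2. The sentence just before the censoring rule counts any event treatment-emergent under OKZ, and Section 9.4.6.1.1 leaves that open-ended. The claim about the rates then relies on the open reading of the same term. The text is ambiguous, but it does not show two biases in opposite directions.

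Nor do the rules give three different dates for every subject. They coincide on the nominal schedule, and data collection bounds the numerator in practice. The documents also do not say that contact to follow an old AE counts as last contact for analysis. All of this stands, and it limits the size of the first point.

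Two further replies carry less weight. All analyses are descriptive, so an empty 30-month cell is a blank rather than a false result. That is fair, but uncapped last contact could put a few late-contact subjects at risk there and produce a value resting on almost nobody. Section 9.4.6.1.2 also leaves further details to the SAP, and no separate SAP text is in the document reviewed. However, the censoring date and landmarks are already fixed in the section, so a SAP would have to override them rather than fill a gap.

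**Conclusion.** The concern holds as an inconsistency of definition and as landmarks that the schedule cannot supply. It does not hold as a demonstrated bias.

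The rules differ by at most 6 days per subject within the visit window, under 1% of follow-up, and less than one expected MACE under the assumed rates. The gap would be longer only if later AE-follow-up contact counts as last contact. What remains is a real ambiguity for any MACE or malignancy after day 155, and a rate numerator without matching person-time for such an event.

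The landmark finding is firmer because it is calendar arithmetic. It assumes a last dose at Week 104 and calendar months. On that schedule nobody is at risk at 30 months in any group, nobody in e, f, i or j is at risk at 24 months, and the 127-week limit fits only groups c and d and the aggregates a and b that contain them. To say that a 30-month estimate cannot exist would go too far, since uncapped late contacts could produce one. It would not be informative.

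**What to change.** 1. In Section 9.4.6.1, define one end of OKZ follow-up: the earlier of last contact and last dose plus 155 days.
2. Use it as the end of the OKZ treatment-emergent window, as the rate denominator end (unchanged), and as the Kaplan-Meier censoring date for MACE and malignancy.
3. List events after that date separately, including late SAEs reported as possibly related.
4. Drop the 30-month landmark. Report landmarks only within each group's attainable follow-up: for example, up to 24 months in c, d, g and h and in aggregates a and b, and up to 18 months in e, f, i and j. Footnote that at 24 months the aggregates contain only subjects from c, d, g and h.
5. Replace the single 127-week limit by a limit within each group's follow-up, and print it beside the mean, because means over different limits are not comparable.

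The cost is one definition and a revised list of time points and limits. No new data, visits or subjects are needed.
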